## 4.7 Analysis of safety (key secondary endpoint)

### 4.7.1 Adverse events

AEs relating to mothers (study subjects) will be coded using the latest available version of MedDRA. An overall summary table will be provided showing the number and percentage of subjects, within the SAF analysis set, with any:

- Treatment-emergent adverse events (TEAEs)
- Severe TEAEs
- Vaccine related TEAEs
- Vaccine related severe TEAEs
- Treatment-emergent SAE
- Treatment-emergent vaccine related SAEs
- TEAEs leading to withdrawal
- TEAEs with outcome death

The frequencies of the following key secondary safety endpoints will be tabulated in descriptive frequency tables:

- Treatment-emergent solicited injection site reactions
- Treatment-emergent solicited systemic AEs
- All treatment-emergent AEs
- For solicited events and reactions the summary tables will furthermore be presented by vaccination number/visit.

Treatment emergent AEs will be tabulated by system organ class and preferred term and treatment using the latest MedDRA coding.

All treatment emergent events will be listed. Non-treatment emergent events (if any) will be listed separately.

### 4.7.2 Adverse events and other safety assessments in babies.

AEs in babies will be analysed and presented similarly to AEs in mothers, described above.

With respect to the babies, the following set of safety information will likewise be tabulated for all relevant Visits (8, 9, 10, 11) in descriptive summary tables (BSA analysis set):

- Gestational age
- Weight

- Length
- Head circumference
- Apgar score at 1, 5 and 10 minutes
- Developmental milestones at 6 months of age

#### 4.7.3 Safety laboratory assessments

Treatment groups are compared with respect to safety laboratory tests, urinalysis, and vital sign measurements, considering clinically significant results and evaluation of change from baseline, using descriptive statistics.

Absolute values and change from baseline in haematology and clinical biochemistry parameters will be summarized by visit and treatment group using descriptive statistics.

Frequency and percentage for categorical urinalysis data will be presented by visit and treatment group, when relevant.

Laboratory values will be flagged if outside the reference range.

A listing of abnormal values will be presented.

Descriptive statistics for vital signs parameters (systolic and diastolic blood pressure, heart rate, and body temperature) and weight will be presented in the same way as the laboratory parameters.

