#### **Clinical laboratory abnormalities and other abnormal assessments as AEs or SAEs:**

Abnormal laboratory findings (e.g., clinical chemistry, haematology, and urinalysis) or other abnormal assessments (e.g., vital signs) that are judged by the investigator as clinically significant will be recorded as AEs or SAEs if they also meet the definition of a SAE.

Clinically significant abnormal laboratory findings or other abnormal assessments that are detected during the study or are present at baseline and significantly worsen (in intensity or frequency) following the start of the study will be reported as AEs or SAEs.

A pre-existing condition (i.e., a disorder present before the AE reporting started and noted on the medical history/physical examination form) should not be reported as an AE unless the condition worsens (in intensity or frequency) during the AE reporting period.

The reasonable suspected **causal relationship** of an AE to an investigational product is assessed using the following terms:

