### **7.10.2 Safety laboratory assessments, urinalysis and vital signs**

Treatment groups are compared as regards safety laboratory tests, urinalysis, and vital signs measurements, presenting severe (grade 3) or greater results, according to the FDA toxicity grading scale, as well as clinically significant results, as assessed by the investigators, and evaluation of changes since baseline, as applicable, using descriptive statistics. More details will be included in the SAP.

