## 7 Deviations from protocol

- An exploratory analysis of weight of infant over time is added.
- Adverse events in babies are added as secondary safety endpoint(s).
- Central monitoring is described in some detail, but no specific analysis of monitoring data is defined.

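### SAP 4.7.3 omits the protocol's summary of grade 3 or greater laboratory, urinalysis and vital-sign results, and SAP section 7 does not declare the change

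*SAP*

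**What the plan says.** Protocol 7.10.2 compares groups on safety laboratory tests, urinalysis and vital signs by "presenting severe (grade 3) or greater results, according to the FDA toxicity grading scale", together with results that investigators assess as clinically significant and changes since baseline. The comparison is descriptive. The section ends "More details will be included in the SAP".

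SAP 4.7.3 restates the comparison as "considering clinically significant results and evaluation of change from baseline, using descriptive statistics". It then adds:

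- "Absolute values and change from baseline in haematology and clinical biochemistry parameters will be summarized by visit and treatment group using descriptive statistics"
- "Laboratory values will be flagged if outside the reference range"
- "A listing of abnormal values will be presented"
- frequencies for categorical urinalysis data by visit and group
- vital signs and weight, presented in the same manner as the laboratory parameters.

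SAP section 7 lists three departures from the protocol: an infant weight analysis, adverse events in babies as a safety endpoint, and a description of central monitoring. Both documents place laboratory tests, urinalysis and vital signs among the mother's key secondary safety endpoints (Protocol 3.6, SAP 1.1.2.2).

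**The concern.** The protocol's closing sentence hands detail to the SAP. It does not hand over the choice of whether to present graded results. The SAP describes itself in its introduction as elaborating protocol version 5.0, yet it leaves out one of the three elements without saying so.

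The missing element is the only one of the three that sorts results by severity against a common external rule. Clinical significance is an investigator's call, made at 10 sites in three countries (SAP 2.1). A reference-range flag shows that a value is outside the range but not how far. Protocol 4.1 allows testing at site laboratories or a central laboratory, and Protocol 4.5 allows normal ranges to be updated during the study, so a flag need not mean the same thing across laboratories or over time.

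The early unblinded analysis in SAP section 6 uses the methods of SAP section 4 and includes key secondary safety up to Visit 8. Protocol 2.5 says that one regimen will be chosen for phase III on cord-blood immunogenicity and safety results. A gap in SAP 4.7.3 therefore carries into the output that informs that choice.

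**Working it through.** The point is a comparison of texts. The plan gives no figure to reproduce.

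**Step 1. The protocol's elements against SAP 4.7.3.**

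| Protocol 7.10.2 element | In SAP 4.7.3? |
|---|---|
| Grade 3 or greater on the FDA scale | No |
| Investigator-assessed clinically significant results | Yes |
| Change since baseline | Yes |

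Carried over: 2 of 3. Declared in SAP section 7: 0 of 1.

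**Step 2. Is the graded summary elsewhere in the SAP?** In the SAP text, FDA appears only in the change log, as the reason for a revision. Grade 3 appears only in section 5, for adverse events followed under central monitoring. No toxicity scale is named for any analysis.

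**Step 3. Does any remaining output give the number of women per group with a severe value?**

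- *Descriptive statistics.* SAP 4.1 requires minimum and maximum, so the most extreme value per parameter, visit and group will be visible. An extreme beyond a grade 3 limit shows that at least one woman reached it. In a group of 60, the extreme alone fits any count from 1/60 = 1.7% to 60/60 = 100%. Across the six scheduled post-baseline draws (Visits 2 to 7, Protocol Table 2), six severe extremes could come from one woman (1/60 = 1.7%) or from six (6/60 = 10%).
- *Range flags.* These carry no severity.
- *Listings.* These hold the individual values from which a count could be made, but the SAP specifies no such count.
- *Severe adverse event tables (SAP 4.7.1).* Under Protocol 6.1, abnormal findings "judged by the investigator as clinically significant will be recorded as AEs or SAEs". A laboratory value therefore reaches these tables only after an investigator's judgement, and its intensity is then rated as an adverse event.
- *Central monitoring (SAP section 5).* Severe vital-sign outliers are watched, but SAP section 7 says that no particular analysis of monitoring data is defined.

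None of the five gives the count.

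**Step 4. Does the FDA scale's other use fill the gap?** Protocol 6.1 makes it the basis for rating solicited injection-site reactions, fever and solicited general reactions. That use does not extend to laboratory values.

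**The case against.** The strongest reply is that little information is lost. SAP 4.7.3 summarises absolute values as well as changes, SAP 4.1 reports extremes and says that all data will be listed, solicited reactions and severe adverse events stay tabulated, and confirmed Hy's Law cases must be reported as serious adverse events. The analysis is descriptive, with no test or decision rule, and the table could be produced later from data already held. All of this stands and limits the harm. It does not supply a by-group count.

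Four stronger readings are tempting, and the documents do not support them.

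- *Key secondary safety as a whole rests on investigator judgement and range flags.* Only the laboratory, urinalysis and vital-sign part is affected.
- *The SAP output could never show that no grade 3 values occurred.* Where a limit is an absolute value, extremes inside it at every visit would show exactly that.
- *The loss can be sized by counting every planned laboratory result.* The documents do not say how many parameters the scale can grade. Also, Groups 1 and 4 receive saline at Visit 1, so their Visit 2 draw, and their Visit 3 draw if taken before that day's injection, precede any vaccine.
- *The sponsor has decided to drop the summary, so the report will lack it.* The SAP never withdraws it, and an accidental loss of wording fits equally well. The table shells are a separate document (SAP section 10) and may include it. Protocol 7.3 requires departures from planned analyses to be described and justified in the study report.

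**Conclusion.** The point holds as a gap between two current documents. A by-group summary that the protocol specifies is absent from the SAP text, and the absence is undeclared. Its size is one of three protocol elements, confined to the laboratory, urinalysis and vital-sign part of key secondary safety. What is missing is an objective count of women with severe values in each group. The underlying data and their extremes are still reported.

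This should be corrected, but it does not threaten the trial's conclusions. The finding rests on the SAP text alone. If the separate table shells already contain a graded table, the remaining work is to bring the SAP wording into line with them.

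**What to change.** In SAP 4.7.3, restore for each treatment group the number and percentage of women with any post-baseline result of grade 3 or greater, for each laboratory, urinalysis and vital-sign parameter that can be graded on the scale the protocol names. Name the scale and list the gradable parameters. Show baseline grade beside the count for context. A by-visit version is optional and should be a separate display, because a worst post-baseline grade is taken over all visits.

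If the sponsor means to leave the summary out, list the removal in SAP section 7 and justify it.

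The cost is one derivation and one or two extra tables from data already collected. The drawback is that some grades will reflect normal pregnancy. The saline group helps to interpret them, though with 30 women it gives only a rough reference.

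The change should be in place before the early analysis, or the by-group count should be added to that analysis if it has already been run.

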#### 4.8 Analysis of weight of infant (exploratory endpoint)

Weight of the infant is not considered an endpoint in the protocol. It is however measured on four occasions and since weight of newborns is generally considered of medical importance weight will be made, comparing the 5 treatment groups (including group 5). The change-from-baseline (birth) in infant weight will be analyzed using a simple random effects model. Pseudo code related to the implementation of this model:

```
proc mixed data = weight data;  
  class subject group visit region;  
  model change_weight = birth_weight region group*visit / ddfm=sat;  
  random intercept / subject=subject;  
  lsmeans group*visit / diff cl obsmargins;run;
```

*Change\_weight* is the change from baseline in weight and *visit* is the study Visit (i.e., 9, 10, 11). Least square mean estimates of change from baseline in weight with 95% confidence intervals (CI) will be presented at each visit for each vaccination group. Estimated group differences at visit 11 between vaccination groups along with associated 95% confidence intervals and p-values will be presented. Estimated least square means and associated 95% CI of change from birth weight will be plotted over time, by vaccination group.

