#### **4.3.3.3 Physical examinations and vital signs in mothers and babies**

As part of the safety assessments, for the mothers, there is a full physical examination (respiratory, cardiovascular, gastrointestinal, gross central nervous system, gross musculoskeletal) at screening and at 6 months post-delivery, and targeted physical examinations (respiratory, cardiovascular) before each administration of vaccine, and 28 days post-delivery.

Obstetric examinations [fundal height (no fundal height at visits 2, 4 and 6), foetal movement and foetal heart rate] is performed at all pre-delivery visits for mothers.

Vital signs (heart rate, blood pressure and oral temperature) are measured at all study visits for mothers. At the study visits where vaccine is administered, the vital signs are measured before the vaccination and again 30 minutes post-vaccination prior to leaving the site.

At all vaccination visits the injection sites will be inspected and assessed by the site staff before the subject leaves the site. Photographs may be taken, as required to document unexpected reactions.

In case of identification of a new medical condition (or an increase in intensity/frequency of a condition existing at screening) in the mothers, these will be recorded as AEs, as specified in Table 2.

At birth babies are physically examined and weight, length, head circumference and Apgar score at 1, 5 and 10 minutes, as available, are measured. The babies are physically examined at all baby study visits, as specified in Table 3.

In addition to physical examinations, baby assessments include developmental milestones (age-appropriate developmental milestone checks) and vital signs (heart rate), at all baby study visits after birth, assessing the safety and wellbeing of the babies. If medical conditions are identified in the babies, these will be recorded as AEs, as specified in Table 3.

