#### 1.1.1 Objectives

##### 1.1.1.1 Primary objective: immunogenicity

The primary objective of this study is to compare the concentrations of IgG specific to the Alp proteins (RibN, Alp1N, Alp2N and AlpCN) in cord blood from babies, born to women who received the GBS-NN/NN2 vaccine or placebo, between four vaccination regimens during pregnancy, between the GBS-NN/NN2 and placebo groups:

- Group 1: GBS2 doses GBS-NN/NN2 at 26 & 30 weeks GA, placebo at week 22
- Group 2: 2 doses GBS-NN/NN2 at 22 & 26 weeks GA, placebo at week 30
- Group 3: 2 doses GBS-NN/NN2 at 22 & 30 weeks GA, placebo at week 26
- Group 4: 1 dose GBS-NN/NN2 at 26 weeks GA, placebo at weeks 22 & 30

Furthermore, a pure placebo group (with half the number of subjects) has been added for general reference:

- Group 5: Placebo at 22, 26 & 30 weeks GA

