## 4.4 Demographics, baseline characteristics and concomitant medications

### 4.4.1 Demographics data and medical history

Demographic data for mothers contain age at delivery, race, weight, height, BMI, gestational age at randomization. Demographic data for babies: height, weight, gestational age, and gender. Tabulations of these data are performed by treatment group.

- Medical history and concomitant illness will be summarised by SOC and PT for MedDRA version 23.1 or later. The table will display the total number of subjects with medical history, the percentage of subjects (%) with a reported medical history and the number of illnesses reported and will be presented by SOC sorted alphabetically and PT sorted in decreasing frequency of occurrence.
- Prior and concomitant medication will be tabulated separately and summarized by WHO Drug Dictionary terms (version WHODRUG Global C3 September 1, 2020, or later). The table will display the total number of subjects with medication, the percentage of subjects (%) with medication and the number of medications and will be presented by ATC level 4 sorted alphabetically and preferred names sorted in decreasing frequency of occurrence. Prior and concomitant medications are defined as follows:
  - Prior medication: Any medication episode initiated prior to the start of treatment (IMP)
  - Concomitant medication: Any medication episode initiated during the treatment period
- Viral serology – eligibility data regarding Human Immunodeficiency Viruses (HIV) and hepatitis B and C

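### The exploratory infant-weight model in SAP 4.8 estimates postnatal gain given birth weight, not the effect of vaccination in pregnancy on weight, and its random intercept imposes one variance on Visits 9 to 11

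*SAP*

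**What the plan says.** SAP 4.8 justifies the analysis by the medical importance of newborn weight. The outcome is change from birth weight at Visits 9, 10 and 11. The fixed part of the model is "model change_weight = birth_weight region group*visit / ddfm=sat" and the only covariance statement is "random intercept / subject=subject". On reporting: "Estimated group differences at visit 11 between vaccination groups along with associated 95% confidence intervals and p-values will be presented". Least-squares means with 95% intervals are also planned at each visit.

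On timing, Protocol 4.3.3.3 states: "At birth babies are physically examined and weight, length, head circumference and Apgar score at 1, 5 and 10 minutes, as available, are measured". The injections come earlier; for example, SAP 1.1.1.1 has "Group 3: 2 doses GBS-NN/NN2 at 22 & 30 weeks GA, placebo at week 26". Protocol 7.8 expects delivery about 18 weeks after the first dose.

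Other reporting of infant weight is descriptive. SAP 4.4.1 has "Demographic data for babies: height, weight, gestational age, and gender. Tabulations of these data are performed by treatment group", SAP 4.7.2 tabulates weight at Visits 8 to 11, and Table 5 in SAP 6 lists it for the early analysis.

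SAP 4.8 also says "Weight of the infant is not considered an endpoint in the protocol". Protocol 3.6 and SAP 1.1.2.2 both list weight among the key secondary safety endpoints in the baby.

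**The concern.** A baseline covariate is normally fixed before treatment starts. Birth weight is not: exposure is during pregnancy, so birth weight is itself a possible outcome of vaccination. Conditioning on it takes out of the group contrast whatever part of a prenatal effect is already present at birth. The one weight comparison for which the SAP spells out a model, intervals and p-values thus answers a postnatal question, although the reason given for it is newborn weight. A small Visit 11 difference could be misread as reassurance about the effect of vaccination on weight.

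The second issue is the covariance. Visits 9 and 11 fall 24–32 and 166–194 days after delivery. A random intercept alone forces weight change to have the same variance at both. If the spread is larger at six months, the intervals and p-values at Visit 11, the visit at which group differences are promised, are too optimistic.

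**Working it through.** The documents give no SD, effect size or power for infant weight, so there is no plan figure to reproduce. All weight values below are assumptions. The group sizes (60/60/60/60/30), visits, covariates and two-sided 5% level come from the documents.

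**1. Change score or raw weight makes no difference.** With birth weight as a covariate, subtracting it from the outcome only moves its slope by 1. In one simulated set of 270 infants, the Group 1 v 5 contrast at Visit 11 was −0.2093 (SE 0.1246) under both codings, with slopes −0.1695 and 0.8305. The model is an ANCOVA of later weight given birth weight.

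**2. What the contrast estimates.** Let d be the group difference in birth weight, s·d the difference in attained weight at Visit 11, and b the within-group slope of attained weight on birth weight (one slope for all visits, as in the model). The adjusted difference is s·d − b·d = d(s − b).

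For d = −0.20 kg, the table gives the formula value and, in brackets, the simulated mean (1,500 trials, Monte Carlo SE about 0.005 kg):

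| | s = 1 | s = 0.5 | s = 0 |
|---|---|---|---|
| Attained difference, kg | −0.20 | −0.10 | 0.00 |
| Contrast, b = 0.5 | −0.10 (−0.101) | 0.00 (0.003) | +0.10 (0.096) |
| Contrast, b = 0.75 | −0.05 (−0.058) | +0.05 (0.053) | +0.15 (0.142) |
| Contrast, b = 1.0 | 0.00 (0.004) | +0.10 (0.103) | +0.20 (0.195) |

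With s = 0.5 and b = 0.75, attained weight is 0.10 kg lower but the model reports 0.05 kg higher. With s = b the contrast is zero.

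**3. One variance for three visits.** In the data set of step 1, the model SE was 0.1246 at every visit although the residual SDs were 0.386, 0.527 and 0.698 kg. In general, the ratio of model SE to true SE at Visit 11 is r = √(mean of the three visit variances) / SD at Visit 11, and the real size of the 5% test is 2[1 − Φ(1.96r)]. Worked example for 1:1.5:2: √((1 + 2.25 + 4)/3)/2 = 1.555/2 = 0.777, so the interval is 22% too narrow and the size is 12.8%. At Visit 9 the same numerator is divided by 1, so that interval is 1.55 times too wide.

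| SD ratio, Visits 9:10:11 | r at Visit 11 | Visit 11 CI too narrow by | Size of 5% test (simulated) | Visit 9 CI too wide by factor |
|---|---|---|---|---|
| 1:1:1 | 1.000 | 0% | 5.0% (4.6–5.4%) | 1.00 |
| 1:1.1:1.2 | 0.919 | 8% | 7.2% (7.2–8.4%) | 1.10 |
| 1:1.25:1.5 | 0.844 | 16% | 9.8% (8.4–10.2%) | 1.27 |
| 1:1.5:2 | 0.777 | 22% | 12.8% (11.4–13.0%) | 1.55 |
| 1:2:3 | 0.720 | 28% | 15.8% (15.2–16.3%) | 2.16 |

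The simulations used within-infant correlations of 0.6 and 0.8, Group 1 v 2 and 1 v 5, and 2,000 trials each. An unstructured covariance gave 4.6–6.0% throughout.

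**4. Why the covariance should not be changed alone.** Suppose b falls over the visits (1.0, 0.75, 0.5), with s = 0.5 and d = −0.20 kg. The Visit 11 target is −0.20 × (0.5 − 0.5) = 0.00 kg. Over 2,500 simulated trials:

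- random intercept, one slope: +0.05 kg
- unstructured covariance, one slope: +0.12 kg
- unstructured covariance, visit-specific slopes: 0.00 kg (0.005)

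With d = 0 and the same slopes, the last option rejected 4.9%, 4.6% and 4.9% of the time for SD ratios 1:1:1, 1:1.5:2 and 1:2:3. The random intercept rejected 5.2%, 12.0% and 15.7%.

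**The case against.** - **The SAP is open about the outcome.** It calls it change from birth, labels the analysis exploratory, and nowhere calls the contrast a prenatal or total effect. Postnatal gain is a legitimate question. This stands, and the model can be kept. But adjustment for birth weight appears only in the code, and the stated reason is newborn weight.
- **Weight is already reported.** It is tabulated by group and visit, in line with the protocol's descriptive approach to safety. This stands and limits the impact. A reader might infer that the plan rules out any interval for a group difference in birth or attained weight. The documents do not support that: SAP 4.1 has a generic sentence on time-dependent tests and modelling where possible, and the table shells (SAP 10) are a separate document. What can be said is that no such comparison is specified.
- **Reversal is speculative.** It needs a vaccine-related deficit that fades faster than ordinary birth-weight differences, and nothing in the documents suggests this. In separate simulations with no postnatal effect and no shared cause of birth and later weight, the contrast averaged −0.005 to +0.009 kg. That is no reversal, but it still hides a birth-weight effect of −0.10 to −0.30 kg.
- **The variance harm is conditional.** It is nil with equal SDs, and 16% rejection needs a threefold rise in SD. This stands.
- **SAP 4.6 is not a clean precedent.** It uses an unstructured covariance for maternal IgG but falls back to AR(1), which also has one variance, and it uses a single baseline slope. The remedy therefore needs its own fallback.
- **The added comparison is imprecise.** For a 0.20 kg difference, 60 v 30, power is 32–61% at birth (assumed SD 0.6–0.4 kg) and 14–25% at Visit 11 (SD 1.0–0.7 kg). This is why intervals rather than tests should carry the result.

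**Conclusion.** The point holds as a minor one, confined to an exploratory analysis. That the Visit 11 contrast is postnatal gain given birth weight follows from the code and the visit schedule alone. The size and direction of the gap from the effect on attained weight, d(s − b) against s·d, depend on d, s and b, which the documents do not give. The single variance is likewise an exact property of the model, while its consequence depends on SDs that the documents do not give.

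The documents do not support the stronger readings that the Visit 11 contrast will have the wrong sign, that its intervals are certainly too narrow, or that a safety signal would go unseen. No primary conclusion rests on SAP 4.8, and birth weight remains visible in the group tables. The statement that weight is not a protocol endpoint contradicts Protocol 3.6 and SAP 1.1.2.2; that is an editorial matter.

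**What to change.** In SAP 4.8:

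- **(a)** Replace the RANDOM statement with a REPEATED statement for visit within subject, `type=UN`, and at the same time replace `birth_weight` with `birth_weight*visit`. Do not make the first change without the second. If the unstructured fit does not converge, fall back to a structure that keeps visit-specific variances, such as ARH(1) or CSH.
- **(b)** Add a model of weight at Visits 8–11 with region and `group*visit`, the same covariance and no birth-weight term. Report group differences with 95% intervals at Visit 8 and Visit 11.
- **(c)** Label the existing model as postnatal gain given birth weight.
- **(d)** Reconcile the sentence on endpoint status with Protocol 3.6 and SAP 1.1.2.2.

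The cost is code and wording, since weight is already collected at Visits 8–11. The gain model goes from 2 to 6 covariance parameters and gains 2 slopes. The added model has 10 covariance parameters, for up to 270 babies.

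The downside is a few more exploratory estimates of limited precision. The 95% half-width is 1.96 × SD × √(1/n₁ + 1/n₂):

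| | 60 v 60 | 60 v 30 |
|---|---|---|
| Birth, assumed SD 0.4–0.6 kg | 0.14–0.21 kg | 0.18–0.26 kg |
| Visit 11, assumed SD 0.7–1.0 kg | 0.25–0.36 kg | 0.31–0.44 kg |
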